The trial will have an 80% statistical power at the 5% level of significance (two sided) to detect a difference in the proportion of subjects receiving increased dose of eltrombopag with a primary response (2 consecutive platelet counts of > 50,000 and an increase of > 20,000 from the study baseline with in the 8 week increased dose window not as a result of rescue treatment) to subjects without a primary response in the placebo group assuming 50% of subjects randomized to active drug will have a response and 5% of subjects randomized to placebo would have a response. The same statistical test will be run for subjects who achieve partial response. An interim analysis was performed after 18 subjects to test for futility and efficacy.

Dose modification during the long term extension portion of the trial will be made on the basis of individual platelet response to a maximal dose of 150mg. All subjects can be monitored at 4 weeks intervals and then can go to every 8 weeks for the remainder of the study at the discretion of the investigator (investigator may require subjects to come in for additional monitoring if deemed necessary).

If the platelet count is > 150,000 ul and < 400,000 ul the daily dose will be adjusted and if > 400,000 ul the medication will be held and monitor will be as per the prescribing information for eltrombopag in the package insert. However, if the P-I determines that adjusting the subject's dose will negatively affect the subject, he or

she may decide not to escalate or reduce the subject's dose. Circumstances in which this may occur include, but are not limited to: investigator is tapering other medications or the subject has a viral infection. Viral infections have been known to both increase and decrease platelet count in patients with ITP. It is suggested that the increased presence of inflammatory molecules during a viral infection increases platelet production, causing platelet count to increase. Alternatively, platelet count may decrease by virtue of activating the reticuloendothelial system causing greater phagocytosis of antibody-coated platelets and/or platelet production.

Laboratory/Assessment Testing

Please see Appendix 1 for Schedule of Events.

Screening

CBC with Differential
Reticulocyte Count
Peripheral Smear
CMP (Sodium, Potassium, Bicarbonate, Chloride, BUN, Creatinine, Glucose, Calcium, Total Protein, Albumin, including AST/ALT, Fractionated Bilirubin Level)
Urine Pregnancy Test (when appropriate)

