5. STUDY TREATMENTS

5.1. Treatment Assignment

Subjects will be randomly allocated in a two to one ratio to receive treatment or placebo. Subjects and investigators will be blinded to randomization. Randomization will be stratified according to splenectomy status. Randomization will be performed at the time of informed consent with a computer generated randomization table

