Dose modification during the long term extension portion of the trial will be made on the basis of individual platelet response to as high a dose as 150mg. If the platelet count is > 150,000 ul and < 400,00 ul the daily dose will be adjusted and if > 400,000 ul the medication will be held and monitor will be as per the prescribing information for eltrombopag in the package insert. However, if the P-I determines that adjusting or stopping the subject's dose will negatively affect the subject, he or she may decide not to escalate, reduce, or stop the subject's dose. Circumstances in which this may occur include, but are not limited to: investigator is tapering other medications or the subject has a viral infection. Viral infections have been known to both increase and decrease platelet count in patients with ITP. It is suggested that the increased presence of inflammatory molecules during a viral infection increases platelet production, causing platelet count to increase. Alternatively, platelet count may decrease by virtue of activating the reticuloendothelial system causing greater phagocytosis of antibody-coated platelets and/or platelet production.

Data Collection and Monitoring

Data will be collected and entered into a Microsoft excel eCRF by the clinical research coordinator. Data will be entered into the eCRF after each study visit. The Principal investigator will verify the data quarterly to ensure that the data collected and entered is accurate.

Interim Analysis:

An interim analysis was performed after 18 patients were enrolled in the study. The data suggested that non-splenectomized patients tended to have higher average platelet counts compared to splenectomized patients for the first 8 weeks in the open-label extension phase. When subjects were on active drug, the results revealed that males tended to have a higher complete response rate compared to females. Of note, three subjects were removed due to SAEs, however only one patient was removed because of a study drug related event (elevated LFTs). Further analysis will be performed to evaluate the long term efficacy and safety of Eltrombopag at doses higher than 75 mg after 36 and then 60 patients have completed 8 weeks of active medication.

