8.2. Study Design Considerations

8.2.1. Sample Size Assumptions

The trial will have a 80% statistical power at the 5% level of significance (two sided) to detect a difference in the proportion of patient receiving increased dose of eltrombopag with a primary response (Platelet Count $\geq 50,000$ per cubic millimetre and $> 20,000$ above baseline) to patients without a primary response in the placebo group. assuming 50% of patients randomized to active drug will have a response and 5% of patients

randomized to placebo would have a response. An interim analysis will be performed after 18 subjects to test for futility and efficacy and also to re-estimate sample size. If neither futility nor efficacy are met the trial would continue to enroll. Based on the observed treatment effect at the interim analysis the sample size would be allowed to expand to up to 60 subjects

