8.3. Data Analysis Considerations

8.3.1. Key Elements of Analysis Plan

The analysis would primarily be descriptive except for the primary endpoint. In order to make the study feasible, the current plan for 36 patients does not allow for much flexibility. It does allow for a confirmatory study from the patients on placebo who can then follow the 8 weeks of dose escalation treatment as an open label study (note they will have been on 75 mg of eltrombopag for at least 11 weeks at that time). All secondary analyses will be underpowered but will be descriptive.

Analysis of efficacy will be based on the intention to treat population of all subjects who underwent randomization.

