8.3.1.1. Interim analysis

Results of Interim analysis:

In the interim analysis of 18 subjects, the data suggests that non-splenectomized patients tended to have greater average platelet counts compared to splenectomized patients for the first 8 weeks in the open-label extension phase. When subjects were on active drug, the results revealed that males tended to have a higher complete response rate compared to females.

Of note, three subjects were removed due to SAEs, however only one patient was removed because of a study drug related event (elevated LFTs). Further analysis will be performed after 36 patients and 60 patients are enrolled to evaluate the long term efficacy and safety of eltrombopag at doses higher than 75 mg.

Primary Response Criteria:

Complete Response (CR) will be defined as a 2 consecutive platelet counts $\geq 50,000 / \mu\text{L}$ AND $> 20,000$ more than the baseline platelet count at enrollment within the 8 week increased dose window not as a result of rescue treatment. Partial Response (PR) will be defined as a 2 consecutive platelet counts $\geq 50,000 / \mu\text{L}$ OR $> 20,000$ more than the baseline platelet count at enrollment within the 8 week increased dose window not as a result of rescue treatment. Odds of response will be analyzed using logistical regression for binary response variables.

Secondary Response Criteria:

- Platelet Count \geq 50,000 and $>$ 20,000 above baseline for at least 3 of the last 4 of 8 weeks independent of rescue therapy
- Platelet Count \geq 50,000 /uL and $>$ 20,000 above baseline for any 4 of 8 weeks independent of rescue therapy
- At least One Platelet count \geq 100,000
- Number of weeks with Platelet Counts \geq 50,000 /uL and $>$ 20 from baseline in 8 Weeks reduction of bleeding score from baseline to the last count of the study improvement of HRQoL
- Number of weeks with Platelet Counts $>$ 100,000 in 8 Weeks

Secondary Efficacy Endpoints:

- Dose required achieving first platelet count \geq 50,000 /uL ?and $>$ 20 from baseline
- Average Platelet Count at each dose level
- Bleeding scores using Page score and WHO score
- Use of Rescue Treatment

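### The primary logistic regression has no stated terms and no sparse-data method, although randomisation is stratified by splenectomy and zero placebo responders is more likely than not at 36 patients

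*Combined protocol and SAP*

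**What the plan says.** On randomisation, section 5.1 states: "Randomization will be stratified according to splenectomy status". Section 3.1 says the same. Allocation is 2:1.

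On analysis, section 8.3.1 makes everything descriptive except the primary endpoint. For that endpoint, section 8.3.1.1 says only: "Odds of response will be analyzed using logistical regression for binary response variables". No section names the terms in the model, the test (Wald, likelihood ratio or exact), the interval, or what happens if one arm has no responders. Section 3.1 applies the same test to partial response.

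Splenectomy status and starting platelet count appear in section 2.2, but only as factors for an admittedly underpowered subgroup evaluation. Baseline count also enters the response definition, through the required rise of 20,000.

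On size, section 8.2.1 says: "The trial will have a 80% statistical power at the 5% level of significance (two sided) to detect a difference", and section 3.1 gives the rates: "assuming 50% of subjects randomized to active drug will have a response and 5% of subjects randomized to placebo would have a response". Section 8.3.1 refers to 36 patients. Section 8.2.1 allows expansion to 60, and section 4.1 gives 60.

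**The concern.** Three things meet in that one sentence.

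- **Design and analysis are not tied together.** A stratification factor that predicts outcome normally belongs in the primary model. If it is left out, the test tends to be conservative. The interim results give a hint that it matters: "non-splenectomized patients tended to have higher average platelet counts compared to splenectomized patients".
- **The choice is still open after data have been seen.** Results by splenectomy status are known from the look at 18 patients, and further analyses are planned at 36 and 60. With no terms stated, the covariates could be chosen after comparing results.
- **The named method can fail on the data that the plan expects.** With about one placebo responder in prospect (12 × 0.05 = 0.6 at 36 patients, 20 × 0.05 = 1.0 at 60), ordinary logistic regression may have no finite estimate of the only effect that the trial formally tests.

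**Working it through.** **1. The plan's own figure.** Inputs: 5% and 50% response, 2:1, two-sided 5%, 80% power (sections 3.1, 5.1, 8.2.1). The pooled rate is (0.05 + 2 × 0.50)/3 = 0.35. Placebo patients needed:

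n = [1.960 × √(1.5 × 0.35 × 0.65) + 0.842 × √(0.05 × 0.95 + 0.50 × 0.50/2)]² / 0.45² = (1.145 + 0.350)² / 0.2025 ≈ 11.03, so 12.

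With 24 active, the total is 36. The figure reproduces from an unadjusted comparison of two proportions, so it does not depend on any covariate.

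**2. Chance of an empty placebo cell.**

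- 36 patients: 0.95^12 = 0.540
- 60 patients: 0.95^20 = 0.358

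**3. What ordinary logistic regression then does.** Take 12/24 active and 0/12 placebo. The maximum-likelihood odds ratio is (12 × 12)/(12 × 0), which is infinite. Its standard error diverges too, so the Wald test cannot reject. Wald power is therefore capped near 1 - 0.54 = 46% at 36 patients. Simulation (1,500 trials per case) puts it at 27–33% at 36 patients and 60–64% at 60, whatever covariates are included. For treatment alone, Firth's penalty amounts to adding one half to each cell. The same table then gives (12.5 × 12.5)/(12.5 × 0.5) = 25, with a usable likelihood-ratio test and profile interval.

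**4. Why not simply add covariates to the ordinary model?** Expected responders at 36 patients are 24 × 0.50 + 12 × 0.05 = 12.6, or about 4 for each of three coefficients. In simulation under no treatment effect, the maximum-likelihood likelihood-ratio test with stratum and baseline rejected in 6.5–8.9% of trials, against 3.1–5.1% unadjusted. Firth with the same covariates gave 5.1% and 5.7% at a common response rate of 35%, and 1.5% at 5%. Unadjusted Firth gave 5.2%, 4.7% and 0.9%. The simulation error is about 0.6 points. One fully adjusted Firth case had an upper-tail rate of 3.3% (standard error 0.5) against a nominal 2.5%, so control is good but not exact.

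**5. Power from adjustment.** 36 patients, 2:1, half splenectomised, 1,000 trials per row, standard error about 1 point:

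| Assumed odds ratio: splenectomy / per SD of baseline | Firth, treatment only | + stratum | + stratum and baseline |
|---|---|---|---|
| 1 / 1 | 85.5% | 85.8% | 85.0% |
| 2 / 1.5 | 85.0% | 85.3% | 83.9% |
| 1 / 2.2 | 86.9% | 87.0% | 87.8% |
| 3.4 / 2.2 | 86.1% | 87.6% | 88.8% |
| 3.4 / 4.5 | 86.3% | 87.2% | 92.2% |

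The stratum alone adds 0.1 to 1.5 points. Both covariates change power by -1.1 to +2.7 points, and by +5.9 only when the baseline effect is very strong. A separate run of 1,500 trials with no covariate effect gave 85.3% against 86.9% unadjusted, a loss of 1.6 points.

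**The case against.** **The plan is silent; it does not exclude the stratum.** This stands. A reader might infer that an unadjusted model has been chosen and that real power is being thrown away. The text does not say so: it names a method and lists no terms. The power loss is not established either. The interim evidence gives a direction only. It concerns average counts rather than response, comes from the open-label extension, and involves at most 18 patients. Larger gains appear if the adjusted Firth model is set against Fisher's exact test (about 80–82% power in the cases tabulated). About 4 to 7 points of those come from leaving Fisher, with no covariate in the model, and the plan never mentions Fisher.

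**An unadjusted likelihood-ratio test also copes with an empty cell, and looks more powerful.** Its simulated power at 36 patients is 91.8%, above Firth. This is the strongest objection, and in part it stands: the test statistic stays finite. But some of that power is bought with excess type I error. Summing Bin(a; 12, p) × Bin(b; 24, p) over all 13 × 25 outcomes with a statistic above 3.84 gives a true level of 6.8% at a common response rate of 15% or 20%. For unadjusted Firth the same sum stays at or below 4.5% at the rates checked between 5% and 50%. With no placebo responders, the ordinary test rejects from 5 active responders (statistic 4.45) and Firth from 7 (4.33). The ordinary odds ratio and the upper end of its interval remain infinite in those trials. In any case, the plan does not say that this test would be used.

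**An exact test stratified by splenectomy would be the simpler answer.** It holds its level, and it beats Fisher when the stratum matters. But its power was about 77–82% against 86–93% for the Firth model, so it serves better as a sensitivity analysis.

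**Conclusion.** The gap is real, and it is one of specification. The only confirmatory analysis lacks terms, a test and a sparse-data method; the randomisation stratum is not tied to it; and the named method has no finite odds ratio in 54% of 36-patient trials (36% at 60) under the plan's own rates. Those percentages follow from the documents alone.

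The power effect of adjustment is small: about 0 to 1.5 points for the stratum, and about -1 to +3 points for stratum plus baseline, with more only under a very strong baseline effect. These figures assume a splenectomised share of one half or one third, a normally distributed baseline count, the odds ratios shown and no dropout. None of these is in the documents. At 60 patients, ordinary logistic regression with a likelihood-ratio test has about 98–99% power with or without covariates, so there the case rests on a usable estimate and on pre-specification.

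**What to change.** Before the analysis at 36 patients, replace the sentence in section 8.3.1.1 with a specification of these points:

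- **Primary analysis:** Firth-penalised logistic regression on the intention-to-treat population, with treatment, splenectomy stratum as randomised, and baseline platelet count. Report a two-sided penalised likelihood-ratio test and a profile penalised-likelihood interval.
- **Baseline:** use the same count in the model and in the response definition. Sections 6.3 and 8.3.1.1 take it at enrolment, section 2.1 refers to a study baseline, and section 3.1 lets patients enrol before the three weeks on 75 mg that precede Day 1. State which count is meant, once.
- **Sensitivity analysis:** an exact test stratified by splenectomy status.
- **Not to be used:** covariate adjustment by ordinary maximum likelihood, because of the type I error shown above.
- **Partial response:** the same model, since section 3.1 promises the same test.

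Cost: a paragraph of text and standard software, with no new data. If the covariates predict nothing, the loss is about 1 to 2 points of power, and simulation error of about a point means that it could be slightly more.

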8.3.1.2. Safety Analyses

For safety analysis the population for analysis will include all randomized subjects who received at least one dose of study medication. Subjects will be evaluated according to the treatment they received.

Malignancy

Malignancy will be descriptive

Bone Marrow Reticulin Fibrosis

Bone Marrow Fibrosis monitoring will involve performing bone marrow aspirate and biopsy on any consenting patient who elects to remains enrolled in long term extension after 12 months of therapy. All marrows will be read by Drs [name] and [name] at Weill-Cornell Medical Center.

Re-occurrence of thrombocytopenia

Re-occurrence of thrombocytopenia will be defined as platelet count $<$ 10,000 uL or 10,000 ul decrease from baseline platelet count at enrollment in the 4 weeks following discontinuation of the study medication

Thrombosis

Thrombosis will be descriptive

Drug Induced Liver Injury

Elevations in ALT > 3 time upper limit of normal or bilirubin level > 2 times the upper limit of normal will be monitored and assessed for continuation or stopping of study drug as per Phase II Liver Safety Algorithm (see Appendix)

Incidence of new and progression of previously identified cataracts

Cataract assessment will involve a baseline eye exam in all enrolled patients with subsequent evaluations at 6 months and 18 months in the patients that continue to receive therapy in the long term extension study. If possible re scheduling, all exams will be performed by [name].

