4. SUBJECT SELECTION AND WITHDRAWAL CRITERIA

4.1. Number of Subjects:

60 subjects will be enrolled.

4.2. Inclusion Criteria:

Subject or their parent/ guardian has signed and dated a written informed consent

Males and Females aged 3 year or older, who can swallow a tablet, and are diagnosed with chronic ITP according to the new consensus guidelines (Provan, Blood, 2009) are eligible.

No indication of a disease which may cause thrombocytopenia other than ITP---- no specific testing required

Subjects with thrombocytopenia $\leq 50,000 /uL$ after at least 21 days of daily dosage with eltrombopag 75mg

Stable dosage of concomitant treatments for ITP
 ≥ 2 weeks or longer (corticosteroids);

At least 2 weeks from rescue therapy for ITP (WinRho, IVIG, corticosteroids, platelet transfusion) or 1 week if therapy has clearly been ineffective

At least 4 weeks from rituximab treatment

Pregnant or Lactating Women are excluded

Women of child-bearing age with a negative pregnancy test within 7 days of enrollment and who agree to use acceptable methods of birth control will be eligible for this study

Female subjects or female partners of male subjects must either be of non-child bearing potential (hysterectomy, bilateral oophorectomy , bilateral tubal ligation or post menopausal for more than one year) OR, if of child bearing potential, using one of the following highly effective methods of contraception.
-complete abstinence from intercourse

- Intrauterine device (IUD)
- Two forms of barrier contraception. diaphragm plus spermicide, or for males condoms plus spermicide.
- Male partner is sterile and is the only partner of the female.
- Systemic contraceptives

4.3. Exclusion Criteria:

Previous history of eltrombopag-related LFT elevation that required sustained interruption of treatment

Previous history of immediate or delayed hypersensitivity reaction or idiosyncrasy to drugs chemically related to eltrombopag

Known HIV Infection

History of Arterial or Venous Thrombosis within the past year or requiring ongoing therapy

Known Active Hepatitis C infection

Elevated AST/ALT or Creatinine > 1.5 times upper limit of normal in 4 weeks prior to enrollment*

Abnormalities in WBC, ANC and Hemoglobin > 1.5 times upper or lower limit of normal*

* Subjects can be rescreened to be included

4.4. Withdrawal Criteria:

Subject may withdraw consent at any time

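### The below-10,000 limb of the re-occurrence definition ignores baseline, so a subject who enters below 10,000/µL and is unchanged counts as an event

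*Combined protocol and SAP*

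**What the plan says.** The definition is in Section 8.3.1.2 (Safety Analyses). It opens "Re-occurrence of thrombocytopenia will be defined as platelet count" and sets two alternatives: a count below "10,000 uL or 10,000 ul decrease from baseline platelet count at enrollment in the 4 weeks following discontinuation of the study medication". The reference to baseline belongs to the decrease; the 10,000 threshold is absolute.

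Three other provisions decide who can meet it:

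- **Entry count.** Section 4.2 admits subjects at or below 50,000/µL "after at least 21 days of daily dosage with eltrombopag 75mg". Section 3.1 describes non-responders as below 50,000. Neither gives a lower limit.
- **Population.** Section 8.3.1.2 uses "all randomized subjects who received at least one dose of study medication". It does not restrict the outcome to subjects who had responded.
- **Window.** The outcome is assessed "in the 4 weeks following discontinuation of the study medication". Section 3.1 and Appendix 1 schedule a CBC in each of post-study Weeks 1 to 4.

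The plan states no expected rate, test or power for this outcome. Section 8.3.1 describes the analysis as mainly descriptive apart from the primary endpoint.

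**The concern.** Re-occurrence implies that thrombocytopenia has come back, or is worse once the drug is withdrawn. The stated rule requires neither. It does not ask that the count ever rose on study, and its first limb does not ask that the count be lower than at entry.

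The trial recruits subjects already unresponsive to 75 mg, and some may enter below 10,000. For them the first limb records the disease they came in with. A reader of the safety table could not tell those subjects from subjects whose count fell after the drug was stopped, and the rate would be overstated by an amount the table does not show.

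**Working it through.** There is no plan figure to reproduce, so the check applies the definition to pairs of counts and then sizes the effect.

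**1. The rule.** Let b be the enrollment baseline and p a count in the 4 weeks after stopping.

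- As written: event if p < 10,000 or b − p ≥ 10,000.
- With the conjunction changed: event if p < 10,000 and b − p ≥ 10,000.

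| b | p | As written | With and |
|---|---|---|---|
| 3,000 | 3,000 | event | no |
| 8,000 | 8,000 | event | no |
| 8,000 | 9,500 | event | no |
| 8,000 | 12,000 | no | no |
| 9,000 | 1,000 | event | no |
| 12,000 | 12,000 | no | no |
| 15,000 | 6,000 | event | no |
| 45,000 | 11,000 | event | no |
| 45,000 | 45,000 | no | no |

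Over a grid of baselines, every unchanged count below 10,000 is an event as written, and no unchanged count from 10,000 to 50,000 is. The certain artefact is therefore confined to baselines below 10,000.

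**2. Size of the certain artefact.** Section 4.1 states that "60 subjects will be enrolled". The share f entering below 10,000 is not in the documents, so f is an assumption. With unchanged counts and every subject assessed, automatic events = 60 × f:

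- f = 10%: 60 × 0.10 = 6
- f = 20%: 60 × 0.20 = 12
- f = 40%: 60 × 0.40 = 24

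At the 36 subjects mentioned in Section 8.3.1, the range is 36 × 0.10 = 3.6 to 36 × 0.40 = 14.4, or about 4 to 14.

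**3. Illustration for other baselines.** Here false flags come from variation alone. Assumptions, none from the documents: a stable true count, lognormal within-subject variation with CV 20% to 40%, and a baseline measured with the same variation. The baseline is capped at 50,000 by eligibility, and four post-study counts are taken. The share flagged by the rule as written:

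| True count | Flagged |
|---|---|
| 5,000–8,000 | about 100% |
| 12,000 | 60–87% |
| 20,000 | 9–41% |
| 30,000–45,000 | 24–44% |

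These figures depend on the model. Without the 50,000 cap on the measured baseline, the last row becomes 25–58%. With and in place of or, the share reaches 15% at a true count of 15,000 and CV 40%, or about 25% if the variation is normal rather than lognormal.

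**4. What requiring any fall does below 10,000.** If a subject's true count is stable, the baseline and the four later counts are five exchangeable values. The baseline is the lowest of the five with probability 1/5, so at least one later count lies below it with probability 1 − 1/5 = 4/5. Requiring a count below baseline removes subjects who are unchanged or higher, but does not by itself separate worsening from noise. Subjects with a low baseline therefore need their own row.

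**The case against.** The strongest reply is that this is one descriptive safety tabulation. No test, sample size or stopping rule depends on it, and the weekly counts are collected, so change from baseline can be examined whatever the label says. The rule as written also over-includes rather than under-includes: it captures every observed fall of 10,000 or more. All of that stands, and it limits the importance of the point. It does not make the reported rate interpretable, because no other section excludes low baselines or requires a prior rise.

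A second reply concerns the decrease limb. A fall of 10,000 from baseline is worsening by construction, and calling it ordinary variation rests on a CV that the documents do not supply. That also stands. The simulated percentages are illustrations and do not show that this limb is wrong.

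A reader might infer that the outcome mainly counts persistent disease and noise, or that it hides any real signal. The documents support neither. They give no baseline platelet distribution, so the share of artefactual events is unknown, and the underlying counts remain available.

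**Conclusion.** The point holds for baselines below 10,000/µL. There, an unchanged count, or one that rises but stays below 10,000, is scored as re-occurrence, and nothing elsewhere in the plan corrects this. The inflation is 6 to 24 automatic events in 60 subjects if 10% to 40% enter below 10,000, their counts do not change and all are assessed after stopping. That share is an assumption. For baselines of 10,000 or more there is no certain error, and the false-flag rates depend on the assumed variation.

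A reader might also infer that the or is a slip for and. The text does not show that, and the substitution would be unsound. It misses large falls that stay above 10,000 (45,000 to 11,000), falls of under 10,000 that end below 10,000 (15,000 to 6,000), and any worsening from a baseline below 10,000 (9,000 to 1,000).

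The definition should be corrected, but nothing about the primary endpoint turns on it.

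**What to change.** Amend the analysis definition in Section 8.3.1.2 as follows:

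1. Count the below-10,000 limb only when the count is also below the subject's own enrollment baseline.
2. Report the two limbs separately: a new count below 10,000 from a baseline of 10,000 or more, and a fall of at least 10,000 from baseline.
3. Tabulate subjects with a baseline below 10,000 in their own row, with the size of the change shown, since a small fall among four counts is expected even when nothing has changed.

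This keeps the plan's choice of baseline and uses counts already scheduled. The cost is a slightly longer definition and one extra table row. Sections 6.4.6.2 and 8.3.1.1 report that the interim analysis after 18 subjects has been done, and Section 3.1 unblinds each subject after Part 1. The change should therefore be dated and documented as made after data had been seen. Showing the rate under the present definition alongside would make its effect visible.
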